Additionally, wording clarifications have been made for the interim overall survival (OS) analyses in Part B. If the first interim OS analysis were to reach the statistical significance with approximately 102 events, then the study would stop for early superiority for the formal OS comparison, and second interim OS analysis with approximately 127 events would not be performed. Due to this reason, the scenario with 127 OS events is redundant, and it is now omitted from the protocol to simplify the interim OS analyses plan in Part B. With this update, it is now clearly stated that the interim OS analyses in Part B are to be based on 102 and 146 events, as initially planned.

SUMMARY OF KEY CHANGES FOR PROTOCOL AMENDMENT 06		
Section Number & Title	Description of Change	Brief Rationale
Section 10.1.1 Part A: Combination Comparison of DFS	Typographical error has been updated within the section to align with values presented in Table 10.1.1-1 .	Typographical error has been corrected.
Section 10.1.2 : Part B: Monotherapy Comparison of DFS Table 10.1.2-2 : Part B Summary of Sample Size Parameters and Schedule of Monotherapy (without an Interim Analysis) Section 10.3.4 : Interim Analyses and Hierarchical Testing	Parameters and schedule of analysis for final DFS analysis alone in Part B were added. Also, summary Table 10.1.2-2 was added.	In the event that the target number of events needed for the final analysis is projected in a shorter time interval (approximately within 6 months), the interim analysis of DFS will not be performed and only one final analysis of DFS will be conducted in Part B.

SUMMARY OF KEY CHANGES FOR PROTOCOL AMENDMENT 06		
Section Number & Title	Description of Change	Brief Rationale
Section 10.3.4 : Interim Analyses and Hierarchical Testing	Language of the Part B OS interim analyses is clarified and one of the scenarios for the second interim OS analysis in Part B is omitted.	The Part B OS interim analyses language is updated to clearly state the plan for the pre-specified interim analyses. Also, OS interim analysis with approximately 127 events is a redundant scenario, and it is now omitted.
Section 10.3.1 : Efficacy Analyses	Stratum(s) with small number of participants.	In the event that there are fewer subjects randomized to a stratum, the participants in the stratum will be combined into another stratum.

TABLE OF CONTENTS

TITLE PAGE	1
DOCUMENT HISTORY	3
OVERALL RATIONALE FOR PROTOCOL AMENDMENT 06:	5

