10.3.4 Interim Analyses and Hierarchical Testing

The Statistical Analysis Plan will further describe the planned interim analyses.

Part A Combination Analyses Timing

One formal DFS interim combination analysis will be conducted at the time when approximately 88% (204) of the total DFS events in the combination and placebo arms have occurred and the time when the total enrollment of both Part A and Part B is expected to be complete. This formal comparison of DFS will allow for early stopping for superiority. The stopping boundaries at the interim and final analyses will be derived based on the exact number of DFS events using Lan-DeMets alpha spending function with O'Brien-Fleming boundaries. Note that if Part B enrollment is still ongoing at the time of observing the required number of events for the interim analysis and target number of events needed for the final analysis is projected to occur in a shorter time interval (approximately within 4 months), then the interim analysis of DFS will not be performed and only one final analysis of DFS will be conducted after the completion of enrollment in Part A and Part B (statistical significance of only one final analysis of DFS is 0.05 [two-sided]).

If the DFS combination analysis is significant, the OS combination analysis will be tested hierarchically. Formal OS interim combination analyses will be conducted at the time when the interim or final DFS combination analysis is significant. This formal comparison of OS will allow for early stopping for superiority.

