The OS combination analyses occurring at the time when the DFS combination analysis is significant either after the Part A (approximately 800) participants randomized to the nivolumab + ipilimumab and placebo arms have a minimum of 20 or 26 months of follow-up, which are expected to occur at approximately 56 (62% of the total events) and 62 (70% of the total events) months from study initiation, respectively. These are at equivalent times when the DFS combination analyses of Part A are expected to occur. However, in the situation when the DFS combination analysis is significant at 56 months but OS is not significant at that time, the 62 month DFS analysis will not be necessary and so the second OS combination interim analysis will occur at 70 months (82% of the total events) rather than 62 months (70% of the total events). At the 56- and 62-month (or 70-month) OS combination analyses, approximately 178 and 201 (or 235) events are expected providing 41% and 53% (or 68%) power to detect overall interim OS HRs of 0.68 (P

< 0.009) and 0.70 ($P < 0.012$) (or 0.74, $P < 0.023$), respectively, at the pre-specified alpha level using the Lan DeMets alpha spending function.

The final OS combination analysis will take place after the Part A (approximately 800) participants randomized to the nivolumab + ipilimumab and placebo arms have a minimum of 48 months of follow-up, which is expected to occur approximately 84 months from the start of the study. At the time of the final OS combination analysis, approximately 287 events are expected ensuring 85% overall power to detect a final OS hazard ratio of 0.79 ($P < 0.045$).

Part B Monotherapy Analyses Timing

Similarly, 1 formal DFS interim monotherapy analysis will be conducted at the time when approximately 80% (122) of the total DFS events in the monotherapy and contemporaneous placebo arms have occurred. This formal comparison of DFS will allow for early stopping for superiority. The stopping boundaries at the interim and final analyses will be derived based on the exact number of DFS events using Lan-DeMets alpha spending function with O'Brien-Fleming boundaries. Note that if the target number of events for the interim analysis and final analysis are projected to occur in a shorter time interval (approximately within 6 months), then the interim analysis of DFS will not be performed and only one final analysis of DFS will be conducted (statistical significance of only one final analysis of DFS is 0.05 [two-sided]).

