
If the interim or final DFS monotherapy analysis is significant, the OS monotherapy analysis will be tested hierarchically. The final OS analysis will take place with approximately 182 events among all randomized Part B participants in nivolumab and placebo arms, which is expected to be at approximately 104 months from the start of the study, providing a minimum of 48 months of follow-up. Approximately 182 events are expected, ensuring 44% overall power to detect a HR of 0.73 ($P < 0.045$). Two formal OS interim monotherapy analyses will be conducted, which will allow for early stopping for superiority. The first and second interim analyses of OS are planned to occur with 102 events (56% of the targeted OS events) and 146 events (80% of the targeted OS events) among the randomized participants in nivolumab and placebo arms, which are expected to be at approximately 76 months and 90 months from the start of the study. Approximately 102 and 146 events are expected providing 8% and 27% power to detect overall interim OS HRs of 0.56 ($P < 0.006$) and 0.67 ($P < 0.023$), respectively, at the pre-specified alpha level using the Lan DeMets alpha spending function.

In addition to the formal planned interim analyses for DFS and OS, the DMC will have access to periodic unblinded interim reports of efficacy and safety to allow a risk/benefit assessment. Details will be included in the DMC charter.

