APPENDIX 8 PROTOCOL AMENDMENT SUMMARY OF CHANGE HISTORY

Overall Rationale for the Revised Protocol 05, 13-Feb-2022

The purpose of Protocol Amendment 05 is to address the timing of interim and final disease-free survival (DFS) analyses in Part A, which were initially planned to occur within 6 months of each other. However, the earlier versions of the protocol did not capture the scenario where in which the interim and final analyses of DFS in Part A occurring in a shorter time interval that could occur in the following instances:

- the number of DFS events needed for final analysis can be observed sooner after observing those needed for interim analysis.
- the total enrollment of both Part A and Part B is expected to be complete closer to the date of DFS final analysis and the criteria to conduct the DFS interim analysis (204 DFS events and enrollment close for the study) is not met.

The amendment is based on the need to address how the formal interim analysis of DFS in Part A would be handled for the above scenario.

With a milestone blinded data transfer received from the BICR vendor through the end of January 2022, BMS observed 202 DFS events in Part A. Because the enrollment in Part B was ongoing (and still ongoing at the time of this amendment), the pre-specified criteria to perform the database lock was not met for conducting the interim analysis of DFS in Part A. Consequently, BMS could not proceed with a database lock for the interim analysis of DFS in Part A. The event projections have showed that the target number of events for final DFS analysis is expected approximately within 4 months from the time of observing the events needed for the interim DFS analysis. Due to these reasons, BMS believes that there are operational challenges to perform an interim and final analysis close to one another. However, the scenario to proceed directly to the final DFS analysis in Part A was not pre-specified in the earlier versions of the protocol. As a result, BMS is issuing a protocol amendment to include this scenario with DFS final analysis only. [Table 10.1.1](#) gives details on the alpha, critical hazard ratio, target number of events for the newly added DFS final analysis only scenario in Part A.

This amendment incorporates the changes from the approved Administrative Letters 09 and 10, which are detailed in the Document History but not listed in the Summary of Key Changes below.

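### Part B: the printed final OS threshold, P < 0.045, does not fit OS looks at 102, 146 and 182 deaths; it should be about 0.042

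*Combined protocol and SAP*

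**What the plan says.** Protocol Section 10.3.4 (Part B) tests OS hierarchically once the disease-free survival (DFS) comparison of nivolumab with placebo is significant.

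- **Interim looks.** There are two, each allowing a stop for superiority, at "102 events (56% of the targeted OS events) and 146 events (80% of the targeted OS events"). The printed thresholds are P < 0.006 and P < 0.023, described as set "at the pre-specified alpha level using the Lan DeMets alpha spending function".
- **Final look.** "The final OS analysis will take place with approximately 182 events among all randomized Part B participants in nivolumab and placebo arms". For this look the section states: "Approximately 182 events are expected, ensuring 44% overall power to detect a HR of 0.73", followed by P < 0.045.
- **Spending form.** The O'Brien-Fleming form, and the rule that boundaries follow the events actually observed, are written for DFS: they "will be derived based on the exact number of DFS events using Lan-DeMets alpha spending function". The OS text names Lan-DeMets only and has no matching sentence.
- **Deferral.** Section 10.3.4 opens with "The Statistical Analysis Plan will further describe the planned interim analyses". That separate plan is not in the text reviewed here.
- **History.** The rationale for Amendment 06 records that "the scenario with 127 OS events is redundant, and it is now omitted from the protocol", leaving interim looks at 102 and 146 deaths.

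**The concern.** A look at 80% of the information spends about half of a 5% budget under O'Brien-Fleming spending, so a final level as generous as 0.045 is surprising. Part B DFS shows the contrast: with one interim at 80% of the events, its printed final level is 0.043. Part B OS has a look at the same fraction plus an earlier one, yet its printed final level is higher.

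The number is a decision threshold for a hierarchically tested survival endpoint. If it were applied literally after the DFS gate opened, a final p-value between about 0.042 and 0.045 would be declared significant although the 5% had already been used up.

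**Working it through.** **Inputs.** From Section 10.3.4: looks at 102, 146 and 182 deaths; printed thresholds 0.006, 0.023 and 0.045. From Section 10.1.2: 2:1 allocation, and overall two-sided 0.05 (stated there for DFS, assumed here to pass in full to OS). The O'Brien-Fleming form is also an assumption for OS.

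**1. Spending function.** Information fractions are t = 102/182 = 0.560, 146/182 = 0.802 and 1. The amount spent per side is 2[1 − Φ(2.2414/√t)], where 2.2414 is the upper 0.0125 normal quantile. Doubled, the cumulative two-sided spend is 0.0055, 0.0247 and 0.0500. The correlation between the statistics at looks i < j is √(dᵢ/dⱼ), where d is the number of deaths: √(102/146) = 0.836, √(102/182) = 0.749, √(146/182) = 0.896. Solving for the nominal two-sided levels gives:

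| Look | Printed | Recomputed |
|---|---|---|
| 102 deaths | 0.006 | 0.0055 |
| 146 deaths | 0.023 | 0.0229 |
| 182 deaths | 0.045 | 0.0423 |

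Both interim values are reproduced; the final one is not.

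**2. Does the method reproduce the plan's other thresholds?** Mostly.

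| Analysis (events) | Printed | Recomputed |
|---|---|---|
| Part A OS (178/201/287) | 0.009 / 0.012 / 0.045 | 0.0089 / 0.0123 / 0.0452 |
| Part A DFS (204/232) | 0.034 / 0.041 | 0.0337 / 0.0406 |
| Part B DFS (122/153) | 0.025 / 0.043 | 0.0241 / 0.0429 |
| Part A OS, 70-month look (235, after 178) | 0.023 | 0.0238 |

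The two misses (Part B DFS interim and Part A 70-month look) are about 0.001. The gap at issue is 0.0450 − 0.0423 = 0.0027.

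**3. A check that needs no spending function.** Type I error depends only on the thresholds and the look times. From the trivariate normal distribution with the correlations above:

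- Printed 0.006/0.023/0.045: 5.24%.
- Lowest values that round to those (0.0055/0.0225/0.0445): 5.16%.
- 0.006/0.023/0.042: 4.99%.
- Largest final level that keeps exactly 5%: 0.0421 with interims 0.006 and 0.023; 0.0426 with 0.0055 and 0.0225.

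With both interim looks taken at the printed levels, no final level that rounds to 0.045 keeps 5%.

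**4. Variants.**

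- Spending applied to two-sided 0.05 directly: 0.0088/0.0254/0.0393. This misses both printed interims and lowers the final level further.
- 146 and 182 deaths only: final level 0.0428.
- 102 and 182 deaths only: final level 0.0482. Only leaving out the planned 146-death look makes 0.045 safe.
- The removed schedule 102/127/182: 0.0055/0.0129/0.0453. The last value rounds to the printed 0.045.

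**5. Critical hazard ratio.** HR = exp(−z/√(182 × 1/3 × 2/3)), with √40.44 = 6.360. At 0.045, z = 2.005 and HR = 0.730. At 0.042, z = 2.034 and HR = 0.726. At 0.0423 it is 0.727. All round to 0.73.

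**The case against.** The best defence is that 0.045 is a planning value. It stands in a power statement with approximate event counts. Under a spending function the operative boundary follows the deaths observed, and a team that recomputes would never use 0.045. The SAP, to which the protocol defers, may carry the right value. This limits the practical risk but does not make the printed number correct. The observed-events rule is written for DFS and not for OS, and a correct SAP would then disagree with the protocol.

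A second point concerns which looks take place. OS is tested only after DFS is significant. The 102-death look is expected at about 76 months, the time of the DFS interim, which has 40% power and may be skipped under Amendment 06. If DFS first succeeds at its final analysis (about 84 months), the plan does not say whether the 102-death look counts. If it does not, looks at 146 and 182 deaths with the printed 0.023 and 0.045 give 5.10%, against 5.24% when all three count. So the 5.24% belongs to the path on which the gate opens early. On the other path 0.045 is still too high.

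Third, the link to the removed 127-death schedule is an inference: the current text prints no threshold for it. The finding does not depend on it.

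**Conclusion.** The printed final Part B OS threshold is wrong for the looks now planned: 0.045 should be about 0.042. Used literally with the DFS gate open, the three printed levels give 5.24% two-sided type I error (at least 5.16% allowing for rounding), an excess of about 0.2 percentage points. If the 102-death look does not count, the total is 5.10%. The excess applies only when DFS has already succeeded, and Part B DFS is planned at 60% power.

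The excess over 5% rests only on the printed thresholds, the look times and a full 0.05 for OS. The specific value 0.0423 also assumes the O'Brien-Fleming form, which both printed interims support. If the death counts at the looks drift by about 5%, the recomputed final level ranges from 0.041 to 0.0435, still below anything that rounds to 0.045.

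The fault lies in a printed number, not in the testing strategy.

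A side note on Part A: its 0.045 is fine on the 62-month OS path. It is too high only on the 70-month path (178/235/287 deaths: recomputed 0.0416, total 5.25%). That path needs a significant DFS interim and is very unlikely, since Appendix 8 reports that "the pre-specified criteria to perform the database lock was not met for conducting the interim analysis of DFS in Part A".

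**What to change.** 1. In Section 10.3.4 (Part B), restate the final OS threshold as P < about 0.042. The critical hazard ratio is then about 0.726 and may stay printed as 0.73.
2. Add one sentence, there or in the SAP: OS boundaries are recomputed from the Lan-DeMets O'Brien-Fleming function at the observed number of deaths and for the looks actually taken, as already stated for DFS. This also settles the case where DFS first succeeds at its final analysis, and covers the Part A 70-month path.

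**Cost.** One number, one sentence and about one point of OS power. The plan does not state the true OS hazard ratio behind its power figures, so a range is shown, with looks at 102/146/182 and interim levels 0.006/0.023:

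| Assumed OS HR | Power, final 0.045 | Power, final 0.042 |
|---|---|---|
| 0.70 | 61.9% | 60.9% |
| 0.73 | 51.5% | 50.5% |
| 0.75 | 44.7% | 43.7% |
| 0.78 | 35.2% | 34.3% |

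The change is best made before the OS data mature, so that a final p-value between 0.042 and 0.045 does not start a dispute over which threshold applied.

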12 APPENDICES

APPENDIX 1 ABBREVIATIONS AND TRADEMARKS

Term	Definition
AE	adverse event
ALT	alanine aminotransferase
ANC	absolute neutrophil count
AST	aspartate aminotransferase
AT	aminotransaminases
AUC	area under the concentration-time curve
BMI	body mass index
BMS	Bristol-Myers Squibb
BP	blood pressure
BUN	blood urea nitrogen
C	Celsius
CBC	complete blood count
CFR	Code of Federal Regulations
CI	confidence interval
Cl ⁻	chloride
CLcr	creatinine clearance
COVID-19	Coronavirus Disease 2019
CNS	central nervous system
CRF	Case Report Form, paper or electronic
ctDNA	circulating tumor DNA
DFS	disease-free survival
DMC	Data monitoring committee
ECG	electrocardiogram
eCRF	Electronic Case Report Form
EDC	Electronic Data Capture
eg	exempli gratia (for example)
EOI-PK	end of infusion-pharmacokinetics
ESR	Expedited Safety Report
FDA	Food and Drug Administration

Term	Definition
FSH	follicle stimulating hormone
g	gram
GCP	Good Clinical Practice
GFR	glomerular filtration rate
HBsAg	hepatitis B surface antigen
HBV	hepatitis B virus
HCV	hepatitis C virus
HIPPA	Health Insurance Portability and Accountability Act of 1996
HIV	Human Immunodeficiency Virus
HR	heart rate
HRT	hormone replacement therapy
ICD	International Classification of Diseases
ICH	International Conference on Harmonisation
ie	id est (that is)
IEC	Independent Ethics Committee
IgG	immunoglobulin G
IgM	immunoglobulin M
IMAE	immune-mediated adverse event
IMP	investigational medicinal products
IRB	Institutional Review Board
IRT	Interactive Response Technology
IU	International Unit
IV	intravenous
K ⁺	potassium
kg	kilogram
L	liter
LAM	Lactation amenorrhea method
LDH	lactate dehydrogenase
mg	milligram
min	minute

Term	Definition
mL	milliliter
mmHg	millimeters of mercury
MTD	maximum tolerated dose
µg	microgram
N	number of subjects or observations
N/A	not applicable
NIMP	non-investigational medicinal products
OS	overall survival
PD	pharmacodynamics
PK	pharmacokinetics
SAE	serious adverse event
SARS-CoV-2	severe acute respiratory syndrome coronavirus 2
TAO	Trial Access Online, the BMS implementation of an EDC capability
T-HALF	Half life
Tmax, TMAX	time of maximum observed concentration
WBC	white blood cell
WES	whole exome sequencing
WHO	World Health Organization
WOCBP	women of childbearing potential

APPENDIX 2 STUDY GOVERNANCE CONSIDERATIONS

The term ‘Participant’ is used in the protocol to refer to a person who has consented to participate in the clinical research study. The term ‘Subject’ used in the CRF is intended to refer to a person (Participant) who has consented to participate in the clinical research study.

REGULATORY AND ETHICAL CONSIDERATIONS

GOOD CLINICAL PRACTICE

This study will be conducted in accordance with:

- Good Clinical Practice (GCP)
- as defined by the International Council on Harmonisation (ICH)
- in accordance with the ethical principles underlying European Union Directive 2001/20/EC
- United States Code of Federal Regulations, Title 21, Part 50 (21CFR50)
- applicable local requirements

The study will be conducted in compliance with the protocol. The protocol and any amendments and the participant informed consent will receive approval/favorable opinion by Institutional Review Board/Independent Ethics Committee (IRB/IEC), and regulatory authorities according to applicable local regulations prior to initiation of the study.

All potential serious breaches must be reported to the Sponsor or designee immediately. A potential serious breach is defined as a Quality Issue (eg, protocol deviation, etc) that is likely to affect to a significant degree one or more of the following: (1) the physical, safety or mental integrity of one or more subjects/participants; (2) the scientific value of the trial (eg, reliability and robustness of generated data). Items (1) or (2) can be associated with either GCP Regulation(s) or Trial protocol(s).

Personnel involved in conducting this study will be qualified by education, training, and experience to perform their respective tasks.

This study will not use the services of study personnel where sanctions have been invoked or where there has been scientific misconduct or fraud (e.g., loss of medical licensure, debarment).

INSTITUTIONAL REVIEW BOARD/INDEPENDENT ETHICS COMMITTEE

Before study initiation, the investigator must have written and dated approval/favorable opinion from the IRB/IEC for the protocol, consent form, participant recruitment materials (eg, advertisements), and any other written information to be provided to subjects/participants. The investigator or BMS should also provide the IRB/IEC with a copy of the Investigator Brochure or product labeling information to be provided to subjects/participants and any updates.

The investigator, Sponsor or designee should provide the IRB/IEC with reports, updates and other information (eg, expedited safety reports, amendments, and administrative letters) according to regulatory requirements or institution procedures.

COMPLIANCE WITH THE PROTOCOL AND PROTOCOL REVISIONS

The investigator should not implement any deviation or change to the protocol without prior review and documented approval/favorable opinion of an amendment from the IRB/IEC (and if applicable, also by local health authority) except where necessary to eliminate an immediate hazard(s) to study subjects/participants.

If a deviation or change to a protocol is implemented to eliminate an immediate hazard(s) prior to obtaining relevant approval/favorable opinion(s) the deviation or change will be submitted, as soon as possible to:

- IRB/IEC for
- Regulatory Authority(ies), if applicable by local regulations (per national requirements)

Documentation of approval/favorable opinion signed by the chairperson or designee of the IRB(s)/IEC(s) and if applicable, also by local health authority must be sent to BMS.

If an amendment substantially alters the study design or increases the potential risk to the participant: (1) the consent form must be revised and submitted to the IRB(s)/IEC(s) for review and approval/favorable opinion; (2) the revised form must be used to obtain consent from subjects/participants currently enrolled in the study if they are affected by the amendment; and (3) the new form must be used to obtain consent from new subjects/participants prior to enrollment.

If the revision is done via an administrative letter, investigators must inform their IRB(s)/IEC(s).

FINANCIAL DISCLOSURE

Investigators and sub-Investigators will provide the Sponsor with sufficient, accurate financial information in accordance with local regulations to allow the Sponsor to submit complete and accurate financial certification or disclosure statements to the appropriate health authorities. Investigators are responsible for providing information on financial interests during the course of the study and for 1 year after completion of the study.

INFORMED CONSENT PROCESS

Investigators must ensure that subjects/participants are clearly and fully informed about the purpose, potential risks, and other critical issues regarding clinical studies in which they volunteer to participate.

In situations where consent cannot be given to subjects/participants, their legally acceptable representatives (as per country guidelines) are clearly and fully informed about the purpose, potential risks, and other critical issues regarding clinical studies in which the participant volunteers to participate.

Sponsor or designee will provide the investigator with an appropriate (i.e., Global or Local) sample informed consent form which will include all elements required by ICH, GCP and applicable regulatory requirements. The sample informed consent form will adhere to the ethical principles that have their origin in the Declaration of Helsinki.

Investigators must:

- Provide a copy of the consent form and written information about the study in the language in which the participant is most proficient prior to clinical study participation. The language must be non-technical and easily understood.
- Allow time necessary for participant or participant's legally acceptable representative to inquire about the details of the study.
- Obtain an informed consent signed and personally dated by the participant or the participant's legally acceptable representative and by the person who conducted the informed consent discussion.
- Obtain the IRB/IEC's written approval/favorable opinion of the written informed consent form and any other information to be provided to the subjects/participants, prior to the beginning of the study, and after any revisions are completed for new information.

If informed consent is initially given by a participant's legally acceptable representative or legal guardian, and the participant subsequently becomes capable of making and communicating his or her informed consent during the study, consent must additionally be obtained from the participant.

Revise the informed consent whenever important new information becomes available that is relevant to the participant's consent. The investigator, or a person designated by the investigator, should fully inform the participant or the participant's legally acceptable representative or legal guardian, of all pertinent aspects of the study and of any new information relevant to the participant's willingness to continue participation in the study. This communication should be documented.

The confidentiality of records that could identify subjects/participants must be protected, respecting the privacy and confidentiality rules applicable to regulatory requirements, the subjects/participants' signed ICF and, in the US, the subjects'/participants' signed HIPAA Authorization.

The consent form must also include a statement that BMS and regulatory authorities have direct access to participant records.

Subjects/participants unable to give their written consent (e.g., stroke or subjects/participants with or severe dementia) may only be enrolled in the study with the consent of a legally acceptable representative. The participant must also be informed about the nature of the study to the extent compatible with his or her understanding, and should this participant become capable, he or she should personally sign and date the consent form as soon as possible. The explicit wish of a participant who is unable to give his or her written consent, but who is capable of forming an opinion and assessing information to refuse participation in, or to be withdrawn from, the clinical study at any time should be considered by the investigator.

The rights, safety, and well-being of the study subjects/participants are the most important considerations and should prevail over interests of science and society.

SOURCE DOCUMENTS

The Investigator is responsible for ensuring that the source data are accurate, legible, contemporaneous, original and attributable, whether the data are hand-written on paper or entered electronically. If source data are created (first entered), modified, maintained, archived, retrieved, or transmitted electronically via computerized systems (and/or any other kind of electronic devices) as part of regulated clinical trial activities, such systems must be compliant with all applicable laws and regulations governing use of electronic records and/or electronic signatures. Such systems may include, but are not limited to, electronic medical/health records (EMRs/EHRs), adverse event tracking/reporting, protocol required assessments, and/or drug accountability records).

When paper records from such systems are used in place of electronic format to perform regulated activities, such paper records should be certified copies. A certified copy consists of a copy of original information that has been verified, as indicated by a dated signature, as an exact copy having all of the same attributes and information as the original.

STUDY TREATMENT RECORDS

Records for study treatments placebo infusions (whether supplied by BMS, its vendors, or the site) must substantiate study treatment integrity and traceability from receipt, preparation, administration, and through destruction or return. Records must be made available for review at the request of BMS/designee or a Health Authority.

If	Then
Supplied by BMS (or its vendors):	
Records or logs must comply with applicable regulations and guidelines and should include:
 
 • amount received and placed in storage area • amount currently in storage area • label identification number or batch number • amount dispensed to and returned by each participant, including unique participant identifiers • amount transferred to another area/site for dispensing or storage • nonstudy disposition (e.g., lost, wasted) • amount destroyed at study site, if applicable • amount returned to BMS • retain samples for bioavailability/bioequivalence/biocomparability, if applicable • dates and initials of person responsible for Investigational Product dispensing/accountability, as per the Delegation of Authority Form.

If	Then

Sourced by site, and not supplied by BMS or its vendors (examples include IP sourced from the sites stock or commercial supply, or a specialty pharmacy)
	
The investigator or designee accepts responsibility for documenting traceability and study drug integrity in accordance with requirements applicable under law and the SOPs/standards of the sourcing pharmacy.
 
These records should include:
 
 • label identification number or batch number • amount dispensed to and returned by each participant, including unique participant identifiers • dates and initials of person responsible for Investigational Product dispensing/accountability, as per the Delegation of Authority Form.

BMS or designee will provide forms to facilitate inventory control if the investigational site does not have an established system that meets these requirements.

CASE REPORT FORMS

An investigator is required to prepare and maintain adequate and accurate case histories designed to record all observations and other data pertinent to the investigation on each individual treated or entered as a control in the investigation. Data that are derived from source documents and reported on the CRF must be consistent with the source documents or the discrepancies must be explained. Additional clinical information may be collected and analyzed in an effort to enhance understanding of product safety. CRFs may be requested for AEs and/or laboratory abnormalities that are reported or identified during the course of the study.

For sites using the Sponsor or designee electronic data capture tool, electronic CRFs will be prepared for all data collection fields except for fields specific to SAEs and pregnancy, which will be reported on the electronic SAE form and Pregnancy Surveillance form, respectively. If electronic SAE form is not available, a paper SAE form can be used. Spaces may be left blank only in those circumstances permitted by study-specific CRF completion guidelines provided by Sponsor or designee.

The confidentiality of records that could identify subjects/participants must be protected, respecting the privacy and confidentiality rules in accordance with the applicable regulatory requirement(s).

The investigator will maintain a signature sheet to document signatures and initials of all persons authorized to make entries and/or corrections on CRFs.

The completed CRF, SAE/pregnancy CRFs, must be promptly reviewed, signed, and dated by the investigator or qualified physician who is a subinvestigator and who is delegated this task on the Delegation of Authority Form. Subinvestigators in Japan may not be delegated the CRF approval task. For electronic CRFs, review and approval/signature are completed electronically through the BMS electronic data capture tool. The investigator must retain a copy of the CRFs including records of the changes and corrections.

Each individual electronically signing electronic CRFs must meet Sponsor or designee training requirements and must only access the BMS electronic data capture tool using the unique user account provided by Sponsor or designee. User accounts are not to be shared or reassigned to other individuals.

MONITORING

Sponsor or designee representatives will review data centrally to identify potential issues to determine a schedule of on-site visits for targeted review of study records.

Representatives of BMS must be allowed to visit all study site locations periodically to assess the data quality and study integrity. On site they will review study records and directly compare them with source documents, discuss the conduct of the study with the investigator, and verify that the facilities remain acceptable. Certain CRF pages and/or electronic files may serve as the source documents.

In addition, the study may be evaluated by Sponsor or designee internal auditors and government inspectors who must be allowed access to CRFs, source documents, other study files, and study facilities. BMS audit reports will be kept confidential.

The investigator must notify BMS promptly of any inspections scheduled by regulatory authorities, and promptly forward copies of inspection reports to Sponsor or designee.

RECORDS RETENTION

The investigator (or head of the study site in Japan) must retain all study records and source documents for the maximum period required by applicable regulations and guidelines, or institution procedures, or for the period specified by BMS or designee, whichever is longer. The investigator (or head of the study site in Japan) must contact BMS prior to destroying any records associated with the study.

BMS or designee will notify the investigator (or head of the study site in Japan) when the study records are no longer needed.

If the investigator withdraws from the study (e.g., relocation, retirement), the records shall be transferred to a mutually agreed upon designee (e.g., another investigator, study site, IRB). Notice of such transfer will be given in writing to BMS or designee.

RETURN OF STUDY TREATMENT

For this study, study treatments (those supplied by BMS, a vendor or sourced by the investigator) such as partially used study treatment containers, vials and syringes may be destroyed on site.

If..	Then
Study treatments supplied by BMS (including its vendors)	Any unused study treatments supplied by BMS can only be destroyed after being inspected and reconciled by the responsible Study Monitor unless study treatments containers must be immediately destroyed as required for safety, or to meet local regulations (e.g., cytotoxics or biologics). If study treatments will be returned, the return will be arranged by the responsible Study Monitor.
